Study Protocol

TITLE: The perceptual experience of Argus II users

PROTOCOL NO.: IRB Protocol #20213190

CLINICALTRIALS.GOV ID: NCT05285618

SPONSOR: National Institutes of Health (NIH)

INVESTIGATOR: [name]
[name]
[name]
USA

Subject population

Age range of subject population: 25 – 80

Anticipated number of subjects: 15

Subjects are blind individuals whose vision was restored with the Argus II Retinal Prosthesis System (Second Sight Medical Products, <https://www.secondsight.com>). Argus II is approved for adults of age 25 and up with severe to profound outer retinal degeneration, some residual light perception or the ability of the retina to respond to electrical stimulation, and a history of useful form vision.

We do not control the patient population - patient selection is performed by Second Sight, and eye surgery is performed by qualified eye surgeons at participating clinics scattered throughout the US, Europe, and parts of Asia. Retinal prosthesis patients are extremely rare (~500 patients worldwide).

Inclusion and exclusion criteria:

We will exclude retinal prosthesis patients for whom ophthalmic fundus images and optical coherence tomography (OCT) images show that they will be unable to perform the necessary behavioral tests (many individual differences in the quality of vision produced by these implants is likely due to the health of the individual retina and/or the location of the prosthetic implant). In addition, subjects will be excluded if they cannot perform the behavioral tests for any other reason (e.g. cognitive difficulties).

Recruitment method

All patients will be recruited from our participating sites in the US: Wilmer Eye Institute at Johns Hopkins University (PI: [name]), W. K. Kellogg Eye Center at University of Michigan, Ann Arbor (PI: [name]), and University of Minnesota Health Ophthalmology (Eye) Clinic (PI: [name]).

Each of these sites provides care for 8-15 Argus II patients. A member of the care team will tell the patient about our study using our provided talking points (see attachment) either in person during their next visit to the clinic or on the phone. Should the patient decide to participate in our study, the member of the care team will schedule a visit at the clinic.

Location

Coordinating / administrative site:

- **University of California, Santa Barbara (UCSB):** This is the PI's ([name]'s) institution. No human subject research will take place at UCSB. No PII/PHI data will be shared with UCSB. The PI's team will design the study and analyze the de-identified data collected at the participating sites.

Participating sites:

Human subjects research will be performed at the participating sites in a clinical testing suite of the local eye clinic:

- **Wilmer Eye Institute, Johns Hopkins University.** PI: [name]
- **W. K. Kellogg Eye Center at University of Michigan, Ann Arbor.** PI: [name]
- **University of Minnesota Health Ophthalmology (Eye) Clinic.** PI: [name]

Use of the suite will require the permission of the ophthalmological surgeon who aids with recruitment, and co-ordination with the administrative staff member responsible for managing the ophthalmology clinic.

Identifiable data is used only for recruiting and analyzing ophthalmic records of the patient. Each collaborating site is already set up to store identifiable data of their respective patients. No identifiable patient data will be shared across sites.

Purpose

Objectives. Our goal is to understand and computationally model the perceptual experiences of blind individuals whose vision was restored with retinal prostheses.

Rationale. Degenerative retinal diseases such as retinitis pigmentosa and macular degeneration cause irreversible vision loss in more than 10 million people worldwide. Analogous to cochlear implants, retinal prostheses electrically stimulate surviving retinal cells in order to evoke neuronal responses that are interpreted by the brain as visual percepts.

However, clinical experience with existing retinal prostheses (FDA approved in 2013 under the human device exemption, ~500 implantees) has made it apparent that the vision provided by these devices differs substantially from normal sight. Interactions between implant electronics and the underlying neurophysiology lead to nontrivial perceptual distortions that can severely limit the quality of the generated visual experience. Understanding the causes of these distortions and finding ways to alleviate them will be critically important to the success of this device technology.

Hypotheses. In our prior research, we developed a model that can predict the shape of the visual percepts that implantees see when a single electrode in the array is stimulated

(<https://doi.org/10.1038/s41598-019-45416-4>). However, it is not clear whether this model will generalize to more complex stimulation patterns. We hypothesize that the shape and number of percepts elicited by multi-electrode stimulation depends on the geometric arrangement of activated nerve fiber bundles in the retina. Our model predicts that subjects should see a single phosphene when two activated electrodes stimulate the same optic nerve fiber bundle, and two phosphenes when the two electrodes stimulate distinct nerve fiber bundle.

We further hypothesize that object recognition can be improved by a stimulation strategy that minimizes accidental stimulation of passing nerve fiber bundles in the retina. We will use our computational model to predict which electrodes should be activated to produce a desired percept, and test whether this optimized stimulation strategy can improve behavioral performance.

The purpose of this research is to further our understanding of the visual experience of Argus II users. Clinical experience with existing devices makes it clear that the provided artificial vision differs substantially from normal sight. In the research proposed here, we will combine human behavioral measurements and computational modeling to try to develop better stimulation protocols for retinal implants.

Procedures

Overview. Our experiments are designed to quantify the perceptual experiences of retinal prosthesis patients. We will produce visual percepts in patients either by directly stimulating electrodes (using FDA-approved pulse trains) or by asking them to view a computer or projector screen and using standard FDA-approved stimulation protocols (as is standard for their devices) to convert the computer or projector screen image into pulse trains on their electrodes. All stimulation protocols will be FDA-approved.

Our experiments will follow standard procedures for collecting behavioral data on retinal prosthesis patients. Testing will be carried out within the ophthalmology department of our participating sites, in the clinical testing suite of the ophthalmological surgeon who helped with recruiting the patient. Use of the suite will require the permission of the ophthalmological surgeon who aids with recruitment, and co-ordination with the administrative staff member responsible for managing the ophthalmology clinic.

Methods

Retinal prosthesis setup

The setup for using the Argus II Retinal Prosthesis System (Second Sight Medical Products; Sylmar, CA) is shown in Figure 1 below. The system consists of a 6x10 microelectrode array implanted epiretinally in one eye of the patient, a pair of glasses with a small embedded camera, and a video processing unit (VPU). Stimuli are delivered to the retina as a series of electrical pulse trains (square-wave, charge-balanced) via the various electrodes in the array. The chip is powered wirelessly by the external VPU through magnetic induction. Safeguards to ensure only

FDA-approved stimuli are delivered exist in both software (in the VPU) and hardware form (in the electronics of the implant).

Figure 1: Argus II setup

The setup can be operated in two different modes:

- 1) 'Camera mode': Video captured by the camera on the glasses is sent to the VPU (attached figure, Panel A), which converts incoming frames into an FDA-approved stimulation protocol that is relayed wirelessly to the implant (Panel B). This is how patients use the device in everyday life.
- 2) 'Direct stimulation mode': An external computer is used to specify the pulse trains applied to each electrode (e.g., a 1s 10 Hz cathodic pulse train, with a current amplitude of 100 microAmps and a pulse width of 45 microseconds to Electrode 12) using Second Sight's software suite. Specified stimuli are then sent to the VPU for safety checking, and then delivered to the implant. This mode can only be used by researchers in behavioral experiments.

Stimuli

We will be using the prosthesis setup in both camera mode and direct stimulation mode.

Stimuli will be biphasic square-wave electrical pulses of a given pulse duration, amplitude, and inter-phase gap, or a train of pulses with a given frequency and stimulus duration. None of these stimuli will elicit emotional responses or be aversive in any way.

As mentioned above, the VPU contains software that makes sure that all pulse trains are within FDA-approved safety limits. For example, pulses must be charge-balanced (equal anodic/cathodic charge; so that there is no lasting residual net current in the tissue) and must

have a charge density below 35 microCoulombs/cm² (FDA specification thought to be safe for long-term stimulation).

There are two stages in the software that ensure that these pulse trains must remain within FDA limits: (1) every app in the software suite is based on an FDA approved application programming interface (API) that carries out checks and will “gracefully error” if the specified pulse trains are outside acceptable bounds, (2) the VPU's firmware is programmed to only deliver FDA approved pulses.

The frequency of the pulse train and the current amplitude of the pulse train is not actually a critical safety issue, since the electronic/neural interface is robust to extremely high rates of stimulation and high current levels. However, high frequency pulse trains or high amplitude pulse trains can produce discomfort in patients (analogous to going from a dark movie theater to direct sunlight) due to inducing large-scale neuronal firing. We will normally be focusing on pulse train frequencies/amplitudes that are commonly used by the patient in their everyday lives.

If we use parameters that might be expected to produce a more intense neural response (and therefore have the potential to cause discomfort) we will always introduce them in a step-wise manner (e.g., by gradually increasing the amplitude) while checking that the sensation is not ‘uncomfortably bright’, and we will immediately decrease the intensity of stimulation if patients report that the sensation approaches discomfort.

Tasks

Subjects will be asked to make behavioral judgments in response to single-electrode or multi-electrode stimulation. Examples include detecting a stimulus ('did you see a light on that trial'), reporting size by drawing on a touch screen, reporting shape by selecting a tactile object of similar shape, or identifying what letter has been presented.

We will use standard protocols for collecting behavioral data. The subject will either use verbal report, will draw shapes on a touch screen, or will use the keyboard or keypad attached to a computer as a means of reporting about the stimuli. Both patient response and reaction time will be recorded.

Subjects will sit in a comfortable chair approximately 100 cm from either a computer monitor or a back-projection screen onto which an image is projected using a video projector. Auditory stimuli may be used to cue the beginning of trials/response period. These auditory cues will be at comfortable loudness levels.

Subjects are encouraged to take breaks as often as needed (they may leave the testing room). We use various experimental techniques including: (1) Same-different – e.g. subjects are shown two percepts and are asked if they are the same or different. (2) Method of adjustment – e.g. subjects are asked to adjust a display/stimulation intensity until a percept is barely visible, (3) 2-alternative-forced choice – e.g. subjects will be presented with two stimuli and asked which of the two stimuli is brighter (4) Identification – subjects are asked to identify which letter was presented.

Data collection

At the participating sites, ophthalmological records showing the position of the implant in the eye (fundus photographs) and the height of the implant from the retinal surface (OCT) will be obtained to screen potential subjects. This is necessary because in a significant number of subjects the implant is poorly positioned and the patient will not be able to carry out the required behavioral tests. Prescreening avoids frustration on the part of the patient, and unnecessarily expense (since these patients are not local). If we choose not to enroll a patient or the patient decides not to enroll these data will be immediately destroyed.

Many individual differences in the quality of vision produced by these implants is likely due to the health of the individual retina and/or the location of the prosthetic implant. At the participating sites, fundus and OCT images will be used to estimate the retinal location of the implant. This extracted information will be shared with the coordinating site, which will use these values to inform their computational models.

In some cases, as well as measuring accuracy, we will also measure improvement with practice by repeating the same task across multiple sessions (up to 5 sessions, each carried out on different testing days).

Importantly, identifiable data is used only for recruiting and analyzing ophthalmic records of the patient at each participating site. Each participating site is already set up to store identifiable data of their respective patients. No identifiable patient data will be shared across sites.

The coordinating site will only have access to de-identifiable behavioral results that include phosphene drawings, brightness ratings, behavioral judgments, response times, etc.

Compensation

Subjects will be compensated at a rate of \$20/hour, including travel time. Should a participant withdraw, they will be paid a pro-rated amount per fifteen minutes that they participated in the experiment.

Risks

Psychological

Risk: The main risk in behavioral experiments is fatigue or possible boredom.

Safeguard: If subjects report any of these experiences we will ask the subject to take a break from the experiment until they feel better, and if necessary discontinue the session.

Physical

Risk: There is also a small risk that subjects may get temporary headaches or feel temporary nausea. Patients may experience uncomfortably bright flashes of light.

Safeguard: If subjects report any of these experiences we will ask the subject to take a break from the experiment until they feel better, and if necessary discontinue the session. If we use parameters that might be expected to produce a more intense neural response (and therefore have the potential to cause discomfort) we will always introduce them in a step-wise manner (e.g., by gradually increasing the amplitude) while checking that the sensation is not ‘uncomfortably bright’, and we will immediately decrease the intensity of stimulation if patients report that the sensation approaches discomfort. The PI and collaborators all have at least three years of experience with this approach without incident, and will train all personnel on these protocols.

Confidentiality/Privacy

Risk: Since all our patients are blind, and retinal prosthesis patients are extremely rare, it may be possible to identify individual subjects based on their ophthalmic records.

Safeguard: Private and medical health records will only be used by the participating sites for the purpose of recruitment and device modeling. All information shared with the coordinating site (for the purpose of data analysis and computational modeling) will be de-identified.

Risk: The IRS requires UCSB to report compensation in excess of \$600 per calendar year, which requires the collection of social security numbers.

Safeguard: Social security numbers will exclusively be used for the Form 1099-Misc for Internal Revenue Service (IRS) tax-reporting purposes, and not be associated with the research data.

Data Storage

Data with identifier information is stored exclusively at the participating site as part of the patient’s medical health record, and is managed by the patient’s physician. Importantly, identifiable data will not be shared across sites, which includes the coordinating site.

If necessary, social security numbers will be stored on a HIPAA-compliant UCSB Box account (cloud storage) and will be deleted after the study ends.

Publications will only present de-identified data. We plan to make this data available to academic researchers interested in using the data for either domain or methodological research. Fully anonymized data will be committed to an open-source neuroscience database. Data that cannot be fully anonymized will not be committed to that database.

Autonomy

Risk: Subjects will be compensated at a rate of \$20/hour, including travel time. Should a participant withdraw, they will be paid a pro-rated amount per fifteen minutes that they participated in the experiment.

Safeguard: All participants will receive the same payment regardless of how they are recruited. There will be no deception.

Other

Risk: There are minimal to no risks of harm involved in stimulation of the prosthetic devices as long as standard stimulation protocols are followed.

Safeguard: The prosthetic devices are designed with multiple safeguards to ensure that only safe stimulation protocols can be used. In specific, there are two stages in the software that ensure that stimuli remain within FDA limits: (1) every app in the software suite is based on an FDA approved application programming interface (API) that carries out checks and will "gracefully error" if the specified stimuli are outside acceptable bounds, (2) the VPU's firmware is programmed to only deliver FDA approved pulses. We will use only FDA-approved stimuli.

Consent process

Potential participants will be given the consent form in electronic format so it is processed with text-to-speech technology. During their visit, before we start the experiment, we will read aloud the consent form in its entirety and answer any questions. After all questions are answered and the participant feels comfortable, he or she will be asked to sign if they would like to participate.

Typically, a subject will be accommodated by a sighted person of trust, who will co-sign the consent as an impartial witness. Otherwise a member of the patient's care team or a member of our research team will co-sign as impartial witness.

Once all parties have signed the consent form, the experiment will start. If the participant is not comfortable, they will be free to leave.

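### When a blind subject attends without a companion, a research-team member may sign as impartial witness to a form that the study side has just read aloud

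*Protocol*

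**What the plan says.** The Consent process section of the protocol sets out four steps.

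- Access beforehand: "Potential participants will be given the consent form in electronic format so it is processed with text-to-speech technology".
- Reading at the visit: "During their visit, before we start the experiment, we will read aloud the consent form in its entirety and answer any questions".
- Witness, usual case: "Typically, a subject will be accommodated by a sighted person of trust, who will co-sign the consent as an impartial witness".
- Witness, no companion present: "Otherwise a member of the patient's care team or a member of our research team will co-sign as impartial witness".

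The section closes with "Once all parties have signed the consent form, the experiment will start".

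Two other places bear on the point. The Confidentiality/Privacy paragraph under Risks begins its reasoning with "Since all our patients are blind, and retinal prosthesis patients are extremely rare", so the procedure applies to blind people throughout. The Recruitment method section says "A member of the care team will tell the patient about our study using our provided talking points", and has the same person schedule the visit if the patient agrees.

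**The concern.** The protocol chooses its own standard: the witness is to be impartial. It then lists as eligible a member of the party that is seeking the consent. A research-team member could attest to a reading and to answers that came from colleagues or, since nothing forbids it, from that same person.

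This matters more here than in most studies because the subject cannot see the page at signing. A sighted witness can confirm that the document signed is the one that was read, that the answers agreed with it, and that agreement was given freely. The usual witness comes from the subject's side and is well placed for this. The fallback covers the subject who arrives alone, and there the rule no longer guarantees someone outside the study. The Risks section names headache, nausea, uncomfortably bright flashes and possible re-identification. These are modest, but they are what a subject is agreeing to.

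**Working it through.** No arithmetic applies, since the point depends on no sample size, error rate or effect estimate. The check sets the protocol's statements side by side.

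1. **Who reads and explains.** The Consent process section uses the first person plural and names nobody. Elsewhere in the protocol that pronoun denotes the study side (our experiments, our model, our participating sites). Reading it the same way here is the natural choice, but it remains a reading.

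2. **Who may witness when no companion is present.** There are two options joined by a plain alternative: a care-team member or a research-team member. The care team comes first in the sentence, but no order of preference is stated.

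3. **Whether reader and witness must differ.** No visible statement says so. Steps 1 and 2 together allow three fallback arrangements:
   - a care-team member witnesses a reading by the research side;
   - one research-team member witnesses a reading by another;
   - the same research-team member reads and witnesses.

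   In the second and third, the witness belongs to the party whose conduct is being attested.

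4. **Whether the care-team option is independent.** It can be. The Recruitment method section has one care-team member introduce the study with material that the study supplies. That member is not barred from witnessing, but nothing says that the same person would do so. The protocol also does not say whether the care team and the research team at a site are separate groups.

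5. **Whether a later check exists.** The experiment begins once the signatures are in place, and no independent confirmation after signing is described.

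6. **How many subjects are exposed.** The protocol anticipates 15 subjects; the SAP (Sample Size and Statistical Methods) reports data from 6. The count exposed is the number who came alone and for whom a research-team member, or the person who read the form or introduced the study, signed. Neither factor is given, so the documents fix the count only between 0 and 15 as planned, or 0 and 6 in the analysed data.

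**The case against.** **The default witness is sound, and this is only a fallback.** This is correct and sets the scope. A reader might infer that the consent safeguard as a whole lacks independence. The documents do not support that, because the subject's own companion is the typical witness.

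**A subject who comes alone may still have an independent witness.** Also correct. A care-team member with no part in the consent would serve. A reader might conclude that unaccompanied subjects get no independent check; the text supports only that they may get none.

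**The same person is not said to read and witness.** True. The defect is that separation is not required.

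**The subject has other protection.** The electronic form lets the subject check the wording without relying on the reader. The form is then read in full, questions are answered, signature is sought only when the subject is comfortable, and the subject may leave. This reduces the harm. It does not show that the document signed is the one that was heard, or that the spoken answers matched it.

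**Consent and signature pages are not in the public file.** They may define the witness's role more tightly. If so, the protocol sentence should be brought into line, because as it stands it expressly admits the research team.

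**A headcount would be a guess.** One could suppose that 10% to 40% of subjects come alone, which gives 0.10 × 15 = 1.5 to 0.40 × 15 = 6 of those planned, or 0.6 to 2.4 of the 6 analysed. The documents give no basis for that share. It would also count everyone who came alone, including those witnessed by an uninvolved care-team member.

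**Conclusion.** The point holds for the fallback route only. When a blind subject attends without a companion, the protocol lets a member of the research team act as impartial witness to a form that the study side has just read and explained, and it does not require witness and reader to be different people. The rule therefore fails to secure the property it states. This is a stated rule that misses its own standard, not a missing detail.

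The consequence is that such a subject may have no independent check at signing, mitigated in part by text-to-speech access. The number affected is not known, and the documents do not show that a research-team member ever witnessed. The conclusion assumes that the unnamed reader is on the study side and that no removed page already separates the two roles. Sample size, error rates, outcome and analysis are unaffected; this is a matter of subject protection.

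**What to change.** In the fallback sentence of the Consent process section, delete the words that admit a research-team member. Add that the fallback witness must be a care-team or clinic staff member who did not read the form, obtain the consent or introduce the study to that particular patient. The last condition is specific to the patient: there is no need to exclude every member of staff who helps with recruitment. If some care-team members also belong to the research team, say that they do not qualify.

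The cost is an edit to one sentence, plus minor scheduling when a subject arrives alone. Testing takes place within the eye clinics, so clinic staff are the natural source of a witness, though the protocol does not describe their availability and each site should confirm it.

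The SAP describes the testing of its 6 subjects in the past tense, so the edit can help only further enrolment or reuse of the procedure. For those 6, the sponsor can check from the signed forms who witnessed and, where the records allow, whether that person had also read the form or introduced the study.
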